2. STUDY OBJECTIVES

The purpose of this study is to examine the dapagliflozin treatment regimens of 2.5 mg BID and 5 mg BID as add-on to metformin therapy. The dapagliflozin 10 mg QD treatment group is provided as a measure of assay sensitivity. Comparisons of dapagliflozin 10 mg QD to placebo will be performed with nominal p-values but are not part of the primary or key secondary objectives of the study.

2.1 **Primary objective**

The primary objective of this study is to compare the change from baseline in HbA1c achieved with each of the 2 BID doses of dapagliflozin (2.5 mg BID and 5 mg BID) co-administered with metformin versus placebo co-administered with metformin after 16 weeks of double-blind treatment.

2.2 Secondary objectives

2.2.1 Key Secondary Objectives

Four key secondary efficacy objectives are identified a priori for special consideration in this study, in addition to the primary objective:

- To compare the percent change from baseline in body weight achieved with each of the 2 BID doses of dapagliflozin (2.5 mg BID and 5 mg BID) co-administered with metformin versus placebo co-administered with metformin after 16 weeks of double-blind treatment.
- To compare the change from baseline in fasting plasma glucose (FPG) achieved with each of the 2 BID doses of dapagliflozin (2.5 mg BID and 5 mg BID) coadministered with metformin versus placebo co-administered with metformin after 1 week of double-blind treatment.
- To compare the change from baseline in fasting plasma glucose (FPG) achieved with each of the 2 BID doses of dapagliflozin (2.5 mg BID and 5 mg BID) co-administered with metformin versus placebo co-administered with metformin after 16 weeks of double-blind treatment.
- To compare the proportion of patients with HbA1c <7.0% achieved with each of the 2 BID doses of dapagliflozin (2.5 mg BID and 5 mg BID) co-administered with metformin versus placebo co-administered with metformin after 16 weeks of double-blind treatment, in patients with an HbA1c ≥7.0% at baseline.

2.2.2 Other Secondary Objectives

- To compare the change from baseline in seated systolic and diastolic blood pressure (BP) achieved with each of the 2 BID doses of dapagliflozin (2.5 mg BID and 5 mg BID) co-administered with metformin versus placebo co-administered with metformin after 16 weeks of double-blind treatment.
- To compare the proportion of patients with seated systolic blood pressure <130 mmHg reached with each of the 2 BID doses of dapagliflozin (2.5 mg BID and 5 mg BID) co-administered with metformin versus placebo co-administered with metformin after 16 weeks of double-blind treatment, in patients who had seated systolic blood pressure ≥130 mmHg at baseline.
- To compare the change from baseline in body weight achieved with each of the 2 BID doses of dapagliflozin (2.5 mg BID and 5 mg BID) co-administered with metformin versus placebo co-administered with metformin after 16 weeks of double-blind treatment.

- To compare the change from baseline in HbA1c achieved with 10 mg dapagliflozin QD (once daily) co-administered with metformin versus placebo co-administered with metformin after 16 weeks of double-blind treatment.
- To compare the change from baseline in fasting plasma glucose (FPG) achieved with 10 mg of dapagliflozin QD co-administered with metformin versus placebo co-administered with metformin after 1 week and 16 weeks of double-blind treatment.
- To compare the proportion of patients with HbA1c <7.0% achieved with 10 mg of dapagliflozin QD co-administered with metformin versus placebo co-administered with metformin after 16 weeks of double-blind treatment, in patients with an HbA1c \geq 7.0% at baseline.
- To compare the percent change from baseline in body weight achieved with 10 mg of dapagliflozin QD co-administered with metformin versus placebo co-administered with metformin after 16 weeks of double-blind treatment.
- To compare the change from baseline in body weight achieved with 10 mg of dapagliflozin QD co-administered with metformin versus placebo co-administered with metformin after 16 weeks of double-blind treatment.
- To compare the change from baseline in seated systolic and diastolic blood pressure (BP) achieved with 10 mg of dapagliflozin QD co-administered with metformin versus placebo co-administered with metformin after 16 weeks of double-blind treatment.
- To compare the proportion of patients with seated systolic blood pressure <130 mmHg reached with dapagliflozin 10 mg QD co-administered with metformin versus placebo co-administered with metformin after 16 weeks of double-blind treatment, in patients who had seated systolic blood pressure ≥130 mmHg at baseline.

2.3 Safety objective

To examine the safety and tolerability of dapagliflozin co-administered with metformin versus placebo co-administered with metformin by assessment of AEs, laboratory values, electrocardiogram, pulse, blood pressure, hypoglycaemic events, calculated creatinine clearance, estimated glomerular filtration rate and physical examination findings.

2.4 Pharmacogenetic Objective

To collect and store DNA for future exploratory research into genes that may influence response, eg, safety, tolerability and efficacy of dapagliflozin treatment and genetic factors that may influence susceptibility to type 2 diabetes and/or associated conditions.

3. STUDY PLAN AND PROCEDURES

[figure not shown]
This Clinical Study Protocol has been subject to a peer review according to AstraZeneca standard procedures.

3.1 Overall study design and flow chart

This is a 16-week, international, multicentre, randomised, double-blind, double dummy, parallel-group, placebo-controlled, pivotal Phase III study to evaluate the efficacy and safety of dapagliflozin 2.5 mg BID, 5 mg BID and 10 mg QD in patients with type 2 diabetes. Dapagliflozin or placebo will be added to the therapy of patients who have inadequate glycaemic control on metformin therapy alone.

For the definition of inadequate glycaemic control see Section 4.1, Inclusion Criterion 5.

Figure 1 Study flow chart

Before entry into the study, patients will be screened for an HbA1c level. Patients who meet the HbA1c inclusion criterion can be enrolled and examined for all inclusion and exclusion criteria.

At the start of the open-label treatment (Visit 2), pre-study metformin will be discontinued and replaced with metformin 500 mg tablets provided by the sponsor. In addition, patients will receive two different type of placebo tablets ('double-dummy'), matching placebo for dapagliflozin 2.5 mg and 5 mg (9 mm) BID and matching placebo for dapagliflozin 10 mg

(11 mm) QD (see Section 5.5.2.). The objective of the placebo lead-in period is to ensure that patients are compliant with background therapy, and that only patients who continue to meet the inclusion and exclusion criteria are randomised and receive investigational product or placebo. Criteria for randomisation will be checked at Visit 3.

Upon meeting these criteria, patients will be randomised to the 16-week double blind treatment period.

After either completion of the treatment period, or discontinuation from treatment, patients will enter a 4-week follow-up period. The follow-up visit provides the opportunity to further evaluate changes in physical signs, symptoms or laboratory parameters that may be related to dapagliflozin treatment.

The total planned study duration from Visit 1 to the safety follow-up (Visit 10) will be 25 weeks.

This international study will be conducted at approximately 65 study centres. It is estimated that 940 patients will be screened to achieve 654 enrolled patients, to reach the target of 392 randomised patients during an enrolment period of approximately 6.5 months.

It is expected that 5 to 7 patients will be randomised per centre. Globally patients will be randomised to ensure a 1:1:1:1 ratio of patients in the 4 arms. Recruitment will be competitive between sites and countries. Centres may be discontinued from the study if recruitment rates are poor and new centres may be added if necessary to achieve recruitment goals.

3.1.1 Study Periods

3.1.1.1 Screening Visit

Failure to meet the HbA1c inclusion criterion is one of the main reasons for screening failure in diabetes treatment studies. Discrepancies between locally and centrally determined HbA1c values are common. Therefore, in this study screening activity will comprise submission of one blood sample to determine the HbA1c at the central laboratory.

A screening informed consent form will be provided by AstraZeneca to all the centres, and implemented locally based on all applicable regulatory requirements and laws. The written screening informed consent must be obtained prior to conducting screening visit (Visit S) activities.

Patients will be allowed to proceed to Visit 1 only if they meet HbA1c inclusion criteria (Inclusion criterion 5, Section 4.1). Patients are not allowed to be re-screened.

If the target number of randomised patients within Stratum 1 is reached (up to 20% of randomised patients), communication will be sent out to all sites that screening and enrolment will only continue for patients in Stratum 2 with an HbA1c \geq 7.2% and \leq 10.5% (see Section 4.1, inclusion criterion no. 5, Note 1). For patients in Stratum 2, the randomisation criterion of HbA1c \geq 7.0% and <10.0% will apply (see Section 4.1, inclusion criterion no. 6, Note 2).

Tabla 1

If the target number of enrolled patients for both strata combined is reached, enrolment will be stopped by AstraZeneca in IWRS and central laboratory processing.

All patients who are screened should be listed on a patient screening log, with an S number allocated in consecutive order, having a tick-box for confirmation if the patient was enrolled or not. See also Section 6.2.

3.1.1.2 Enrolment Visit (Visit 1, week –5)

Eligible patients should be seen for Visit 1 within 3 to 14 days after screening. Patients will sign informed consent, undergo repeated check for all applicable inclusion and exclusion criteria, and submit laboratory samples. Diet and lifestyle advice will be given.

The existing patient's metformin medication and dose will remain unchanged. No other antidiabetic drugs are allowed. If applicable, anti-hypertensive medication need to be reviewed and can be adjusted.

3.1.1.3 Placebo lead-in period (Visit 2-3, week –4 to week 0)

Adjustment of metformin dose

At the beginning of the placebo lead-in period (Visit 2, week –4) patients will undergo repeated checks for inclusion/exclusion criteria. Appropriate diet and exercise counselling will be reviewed with all patients at this visit.

At Visit 2, all eligible subjects will stop their original metformin treatment, they will be provided with study drug open-label 500 mg metformin tablets and continue their metformin dose for the duration of the study. Subjects, whose current therapy is not based on 500 mg metformin tablets, will have their dose modified as noted in Table 1.

The open-label metformin dose will remain stable throughout the study. If the metformin dose will require unequal BID dosing, it is up to the investigator and patient to decide when the larger dose should be taken, to decrease the risk of undesired gastrointestinal effects.

| Table 1 Aujustment of metror min dose | | | | | | |
|--|--|--|--|--|--|--|
| If patients' pre-study metformin dose is | Adjust open-label metformin therapy to | | | | | |
| \geq 1500 and \leq 1749 mg/day | 1500 mg/day | | | | | |
| \geq 1750 and \leq 2249 mg/day | 2000 mg/day | | | | | |
| ≥2250 mg/day | 2500 mg/day | | | | | |

In addition, patients will receive two different type of placebo tablets ('double-dummy'), matching placebo for dapagliflozin 2.5 mg and 5 mg (9 mm) BID and matching placebo for dapagliflozin 10 mg (11 mm) QD (see Section 5.5.2.). Placebo will be used to assess subject's compliance with treatment. Subjects should demonstrate good compliance with study medication (\geq 80% and \leq 120%) during the lead-in period. For other subjects the Investigator should ensure that there are no systematic factors which may result in unacceptable

compliance with study medication during the treatment period of the trial, such cases should be discussed with the Study Team Physician prior to randomisation.

At Visit 2, a glucometer and a patient diary will also be provided to patients and they will be instructed to monitor their FPG at least every second day and to enter the results into the patient diary. Investigators may instruct patients to monitor their FPG more often, according to their local treatment guidelines or clinical judgement. For FPG monitoring procedures and assessment of hypoglycaemic events, refer to Section 6.4.10.1.

During the placebo lead-in period, background antihypertensive medications should be adjusted in patients with seated systolic BP \geq 160 mmHg or seated diastolic BP \geq 100 mmHg. Only those patients with seated systolic BP <160 mmHg and diastolic BP <100 mmHg at the end of placebo lead-in period will be randomised.

At Visit 3 assessments are performed primarily to check eligibility for randomisation, following one week later. HbA1c, FPG and CK measured by the central laboratory in a sample taken at Visit 3 will be used for assessment of corresponding eligibility criteria at randomisation.

3.1.1.4 Randomisation and Double-blind Treatment Period (Visits 4-9, week 0 to week 16)

Randomisation visit (Visit 4, week 0)

Eligible patients will be randomised at Visit 4 (week 0, baseline) in a 1:1:1:1 ratio to receive either dapagliflozin 2.5 mg BID, or dapagliflozin 5 mg BID, or dapagliflozin 10 mg QD, or placebo. At Visit 3, one week before randomisation, patients will be stratified based on 1 recruitment factor:

Factor 1: HbA1c value (determined in the blood sample taken at Visit 3, one week before randomisation).

- Stratum 1 (HbA1c <7.0% at randomisation)
- Stratum 2 (HbA1c \geq 7.0% at randomisation)

Stratum 1 is planned to be a maximum of 20% of the randomised patients. If the number of patients in Stratum 1 reaches 20% (n=78) of the total number of planned randomised patients (20% of 392 anticipated is: 78 patients), communication will be sent out to all sites that screening and enrolment will only continue for patients in Stratum 2 with an HbA1c \geq 7.2% and <10.5% (see Section 4.1, inclusion criterion no. 5, Note 1). For these patients in Stratum 2, the randomisation criterion for HbA1c \geq 7.0% and <10.0% will apply (see Section 4.1 inclusion criterion no. 6, Note 2).

Maintenance Treatment Period (Visits 5-9)

Patients will follow up at week 1 (Visit 5), week 4 (Visit 6), week 8 (Visit 7), week 12 (Visit 8) and week 16 (Visit 9) after randomisation, completing the randomised treatment period.

Patients will continue to monitor their FPG levels at least every second day and will continue to enter the results into the patient diary. Investigators may instruct patients to monitor their FPG more often, according to their local treatment guidelines or clinical judgement. Hypoglycaemic events should also be entered into the patient diary. For FPG monitoring procedures and assessment of hypoglycaemic events please refer to Section 6.4.10.1. Diet and lifestyle modification will be reinforced at each visit during the double-blind treatment period.

The following table displays criteria for lack of glycaemic control during the double-blind treatment period. For Visit 6 measurement FPG >240 mg/dL (13.2 mmol/L), and for Visit 8 measurement FPG >200 mg/dL (11.1 mmol/L) will be considered as threshold. Subjects who lack glycaemic control as defined below will be discontinued from the study and will have follow up visit procedures performed. Up-titration of metformin dose during the study will not be allowed.

Table 2Definition of lack of glycaemic control during the randomised
treatment period

| Period | Central Laboratory FPG |
|---|------------------------------|
| From week 1 (Visit 5) to week 4 (Visit 6) | FPG >270 mg/dL (15 mmol/L) |
| From week 4 (Visit 6) to week 12 (Visit 8) | FPG >240 mg/dL (13.2 mmol/L) |
| From week 12 (Visit 8) to week 16 (Visit 9) | FPG >200 mg/dL (11.1 mmol/L) |

Changes in antihypertensive medication may be made as needed for appropriate blood pressure management. All medication changes, including dose modifications and the last blood pressure value measured before a medication change should be recorded in the Electronic Case Report Form (eCRF).

End of Treatment Visit (Visit 9)

Patients will stop taking all study drugs at the end of the treatment period (Visit 9, week 16). The End of Treatment Visit procedures should be performed as soon as possible but at the latest 7 days after discontinuation, for any reason (see Section 4.3.1).

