4.2 Exclusion criteria

Patients must not enter the study if any of the following exclusion criteria are fulfilled.

The following criteria apply to enrolment (Visit 1).

Laboratory value criteria apply at the start of placebo lead in/ open label metformin treatment period (Visit 2, using laboratory values from Visit 1).

Laboratory value criterion no. 27 should be repeatedly checked including at Randomisation (Visit 4, using laboratory value from Visit 3).

Endocrine and metabolic disorders

- 1. Diagnosis of Type 1 diabetes mellitus, known diagnosis of Maturity Onset Diabetes of the Young (MODY) or secondary causes of diabetes mellitus
- 2. History of diabetic ketoacidosis

- 3. Symptoms of poorly controlled diabetes including, but not limited to, marked polyuria, polydipsia, and/or greater than 10% weight loss during the 3 months prior to enrolment
- 4. FPG >270 mg/dL (>15.0 mmol/L)
- 5. BMI >45 kg/m²
- 6. History of bariatric surgery (ie, any surgery to treat obesity; for example, gastric banding or procedures that involve bypassing or transposing sections of the small intestine). History of liposuction is allowed.
- 7. Diabetes insipidus
- 8. Thyroid-stimulating hormone (TSH) and free T4 values outside normal range. An abnormal TSH value needs to be followed up with a free T4 test. Patients with abnormal free T4 values will be excluded. Patients with an elevated TSH and normal free T4 will be allowed if referred to their family doctor for thyroid hormone replacement therapy prior to randomisation.

Kidney disorders

- 9. Creatinine Clearance: <60 mL/min (calculated by Cockcroft-Gault formula) or a measured serum creatinine value of \geq 1.5 mg/dL (133 µmol/L) for male patients and \geq 1.4 mg/dL (124 µmol/L) for female patients
- 10. Urine albumine: creatinine ratio >1800 mg/g
- 11. History of unstable or rapidly progressing kidney disease
- 12. Known condition of familial renal glucosuria

Hepatic disorders

- 13. Severe hepatic insufficiency and/or significant abnormal liver function defined as aspartate aminotransferase (AST) >3X upper limit of normal (ULN) and/or alanine aminotransferase (ALT) >3XULN
- 14. Total bilirubin (TB) >2.0 mg/dL ($>34.2 \mu \text{mol/L}$)
- 15. Positive serologic evidence of current infectious liver disease including Hepatitis B viral antibody IgM, Hepatitis B surface antigen and Hepatitis C virus antibody
- 16. History of drug-induced liver enzyme elevations

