- Major and/or frequent hypoglycaemic events, defined as ≥1 major event or recurring minor events (see Section 6.4.10.1 for definition of minor and major). This definition should be applied after possible contributing factors (eg, excessive physical activity) have been excluded by the investigator
- 11. Pregnancy confirmed by a positive pregnancy test or otherwise verified
- 12. Patients who have an FPG >270 mg/dL (15 mmol/L) between week 4 and week 4 (visits 2 to 6), have an FPG >240 mg/dL (13.2 mmol/L) between week 4 and week 12 (visits 6 to 8), and have an FPG >200 mg/dL (11.1 mmol/L) between week 12 and week 16 (visits 8 to 9). See Section 3.1.1.4, Table 2 for definition of lack of glycaemic control.
- 13. Change in kidney function (Please see Appendix G for further guidance): calculated creatinine clearance <60 mL/min or an increase in serum creatinine of $\ge 0.5 \text{ mg/dL}$

above the baseline value confirmed by a repeated measurement within one week or increase in creatinine that would preclude continued treatment with metformin according to local guidance.

- 14. CK >10xULN confirmed at a repeated measurement preferably within 24 hours, but not exceeding 72 hours, see Section 6.4.14
- 15. Patients with a central laboratory ALT and/or AST >3xULN will be scheduled for a follow-up visit within 3 days following the receipt of the result. See Appendix H for further guidance. Patients should be discontinued from study if the initial and repeat laboratory tests meet any of the following criteria:
 - (a) ALT and/or AST are >3xULN and TB>1.5xULN
 - (b) ALT and/or AST are >5xULN for ≥ 14 consecutive days, at any time after initial confirmatory results
 - (c) ALT and/or AST are >8xULN.
- 16. Serum Sodium \leq 125 mmol/L with or without symptoms; see Appendix F for further guidance
- 17. Since intravascular administration of iodinated contrast agents in radiologic studies can lead to renal failure, metformin should be discontinued prior to or at the time of the test and restarted 48 hours later, after renal function has been re-evaluated and confirmed to be normal.
- 18. Metformin should be discontinued 48 hours before elective surgery with general anaesthesia and should not be resumed within 48 hours of the procedure.

4.3.2 **Procedures for discontinuation of a patient from the study**

Pre-randomisation

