6.4.10.1 Fasting plasma glucose concentrations and hypoglycaemic events

Patient self-monitoring of FPG is performed in order to reduce the risks associated with prolonged hyperglycaemia and to confirm symptoms of hypoglycaemia. Patients will be asked to perform self-monitoring of FPG using glucometers provided by AstraZeneca. The patients will receive instructions for the use of the glucometer according to the manufacturer's instructions.

FPG should be self-monitored at least every second day between visits 2 and 6 and at least once a week between visits 6 and 9. The results should be recorded in the patient diary, which will be collected and reviewed by the study personnel at each visit starting with Visit 3; a print out will be stored in the investigator study file. A new diary will be dispensed to the patient at each of these visits.

The memory of the glucometer should be reviewed and compared with the readings in the patient's diary. The glucose values should be reviewed by the study personnel to identify any unusually high or low values, and to confirm that self-monitoring was performed by the patient. If fingerstick glucose values are discordant with central laboratory results or with clinical symptoms, the patient's glucometer should be tested and the glucometer instructions should be re-reviewed with the patient.

If self-monitored FPG is above 270 mg/dL (15 mmol/L) from week - 4 (Visit 2) up to week 4 (Visit 6), above 240 mg/dL (13.2 mmol/L) from week 4 (Visit 6) up to week 12 (Visit 8), or above FPG >200 mg/dL (11.1 mmol/L) from week 12 (Visit 8) up to week 16 (Visit 9) the patient should repeat the FPG on the same day. If the second FPG measurement is above the stated value, the patient should contact the study centre and be scheduled for a central laboratory FPG measurement within one week.

If central laboratory values confirm that the FPG is above the threshold value, the patient should be discontinued.

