A separate section in the eCRF will be used to document all reported episodes of hypoglycaemia. The patients will be asked to always check their blood glucose if they develop symptoms suggestive of hypoglycaemia and to record specific symptoms in the patient diary. The Investigator is responsible for questioning the patient about all symptoms reported in the diary and for determining if they meet the clinical definition of hypoglycaemia. Only symptoms and/or blood glucose values that meet the definition of hypoglycaemia should be reported on the hypoglycaemia eCRF pages.

A hypoglycaemic event can be either:

- Symptoms of hypoglycaemia with a low blood glucose reading (<63 mg/dL (<3.5 mmol/L))
- A low blood glucose reading (<63 mg/dL (<3.5 mmol/L))
- Symptoms of hypoglycaemia without a blood glucose reading

Hypoglycaemic episodes or discontinuation due to hypoglycaemia should not be reported on the AE eCRF page unless the event fulfils protocol criteria for a Serious Adverse Event (see Section 6.4.2). In this case, an SAE must be reported in addition to the hypoglycaemia eCRF pages for hypoglycaemia.

Symptoms suggestive of hypoglycaemia with an associated capillary or plasma glucose value $\geq 63 \text{ mg/dL}$ ($\geq 3.5 \text{ mmol/L}$), should be recorded as an adverse event rather than as a hypoglycaemic event. If the physician does not consider the glucose measurement to be accurate, however, the event should be documented as a hypoglycaemic event in the hypoglycaemia eCRF.

For the evaluation of hypoglycaemic events, this study will use the definitions provided in the CPMP guidance on clinical investigation of medicinal products in the treatment of diabetes mellitus, as described below.

- **Major hypoglycaemic events,** defined as symptomatic events requiring external assistance due to severe impairment in consciousness or behaviour, with a capillary or plasma glucose value <54mg/dL (<3.0 mmol/L), and prompt recovery after glucose or glucagon administration.
- **Minor hypoglycaemic event**, defined as either a symptomatic episode with a capillary or plasma glucose measurement <63mg/dL (<3.5 mmol/L) regardless of need for external assistance or an asymptomatic capillary or plasma glucose measurement below 63 mg/dL (3.5 mmol/L), that does not qualify as a major episode
- **Events suggestive of hypoglycaemia**, defined as a symptomatic event without a confirmatory blood glucose measurement.

Data to be collected for each **hypoglycaemic** event:

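### The week 4–12 FPG discontinuation limit of 240 mg/dL is printed as 13.2 mmol/L in four places; the correct conversion is 13.3 mmol/L

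*Protocol*

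**What the plan says.** Protocol 3.1.1.4 defines lack of glycaemic control by a central laboratory FPG limit that tightens over the randomised period. The limit for weeks 4 to 12 is printed in four places, each time with the same pair of units:

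- Table 2 in 3.1.1.4: "FPG >240 mg/dL (13.2 mmol/L").
- The text just before Table 2: "For Visit 6 measurement FPG >240 mg/dL (13.2 mmol/L), and for Visit 8 measurement FPG >200 mg/dL".
- Criterion 12 in 4.3.1: "have an FPG >240 mg/dL (13.2 mmol/L) between week 4 and week 12 (visits 6 to 8), and have an FPG >200 mg/dL".
- The self-monitoring rule in 6.4.10.1: "above 240 mg/dL (13.2 mmol/L) from week 4 (Visit 6) up to week 12 (Visit 8), or above FPG >200 mg/dL".

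The consequence is withdrawal. Section 3.1.1.4 says "Subjects who lack glycaemic control as defined below will be discontinued from the study", and 6.4.10.1 says, in slightly softer terms, "If central laboratory values confirm that the FPG is above the threshold value, the patient should be discontinued".

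Section 6.3.1 adds that efficacy laboratory results from baseline onwards, FPG among them, are withheld from the investigator unless they meet the discontinuation criteria of 4.3.1.

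**The concern.** A numerical stopping limit given in two units should be one limit. Here the bracketed mmol/L figure is lower than the mg/dL figure in front of it, so an FPG between the two meets the rule in one unit and not in the other. The value 13.3 mmol/L is printed nowhere for this limit, so cross-reference cannot recover it, and no sentence says which unit governs.

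The figure most likely to matter is the one programmed at the central laboratory. Because 6.3.1 ties release of a post-baseline FPG to the discontinuation criteria, the programmed limit decides both whether the masked value is disclosed and whether the patient leaves the study. If 13.2 mmol/L is entered, a randomised patient slightly below 240 mg/dL could be withdrawn although the mg/dL rule would keep them in. Their week 16 HbA1c would then be carried forward from an earlier measurement (11.2.2 and 12.2).

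**Working it through.** **Inputs.** The glucose pairs printed in the protocol are 270/15, 240/13.2 and 200/11.1 (Table 2), 63/3.5 and 54/3.0 (the hypoglycaemia definitions in 6.4.10.1). Exclusion criterion 4 in 4.2 repeats the first as "FPG >270 mg/dL (>15.0 mmol/L"), and an example of the low-glucose pairs is "Symptoms of hypoglycaemia with a low blood glucose reading (<63 mg/dL (<3.5 mmol/L"). The protocol states no conversion factor. Its own pairs imply about 18 mg/dL per mmol/L (270/15 = 18.00; 200/11.1 = 18.02; 63/3.5 = 18.00; 54/3.0 = 18.00). I use 18, 18.016 and 18.02 to show that the choice does not matter.

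**Step 1: try to reproduce the printed figure.** mmol/L = (mg/dL) / factor.

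- 240 / 18 = 13.33
- 240 / 18.016 = 13.32
- 240 / 18.02 = 13.32

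Each gives 13.3 to one decimal, by rounding or by truncation. The printed 13.2 is not reproduced. In reverse, 13.2 × 18 = 237.6, 13.2 × 18.016 = 237.81 and 13.2 × 18.02 = 237.86 mg/dL.

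**Step 2: compare with the other pairs (factor 18.016).**

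| Printed pair | mmol/L converted back to mg/dL | Gap (mg/dL) |
|---|---|---|
| 270 / 15 | 270.24 | −0.24 |
| 200 / 11.1 | 199.98 | 0.02 |
| 63 / 3.5 | 63.06 | −0.06 |
| 54 / 3.0 | 54.05 | −0.05 |
| 240 / 13.2 | 237.81 | 2.19 |
| 240 / 13.3 (corrected) | 239.61 | 0.39 |

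**Step 3: could one-decimal rounding explain it?** If each mmol/L figure may be off by 0.05, the factor implied by 240/13.2 lies between 240/13.25 = 18.11 and 240/13.15 = 18.25. The row above it in Table 2 (270/15) allows 17.94 to 18.06, and the row below (200/11.1) allows 17.94 to 18.10. No single factor fits all three rows.

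**Step 4: which values are classified differently?**

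| FPG (mg/dL) | mmol/L | To one decimal | >240 mg/dL? | >13.2 (one decimal)? | >13.3 (one decimal)? |
|---|---|---|---|---|---|
| 238 | 13.21 | 13.2 | no | no | no |
| 239 | 13.27 | 13.3 | no | yes | no |
| 240 | 13.32 | 13.3 | no | yes | no |
| 241 | 13.38 | 13.4 | yes | yes | yes |

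With mmol/L compared to one decimal, 239 and 240 mg/dL are affected. Compared unrounded, 238 is as well, because 13.21 exceeds 13.2. With 13.3 printed, the one-decimal rule and the mg/dL rule agree on every row.

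**Step 5: how many values might fall there?** The protocol gives no FPG distribution, so this is illustration only. Assume normal FPG with mean 150 to 180 and SD 30 to 40 mg/dL. The share between 237.81 and 240 then runs from 0.036% (mean 150, SD 30) to 0.740% (mean 180, SD 40). Multiplied by the 392 patients planned for randomisation, that is 0.14 to 2.90 values at one scheduled visit under this limit (Visit 6 or Visit 7).

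**The case against.** The conversion error itself is hard to contest; the argument is about its consequence.

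First, mg/dL comes first and mmol/L is bracketed for every glucose limit, so the natural reading is that mg/dL is the limit and mmol/L a convenience. That is fair and makes a wrong decision less likely, but it is layout and not a rule, and it does not show which figure the laboratory programmed.

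Second, a reader might infer that sites working in different units would withdraw patients differently. The documents do not support this. Table 2 is a central laboratory limit, and 6.3.1 has the criterion applied before a post-baseline value reaches the site. The exposure is a single wrong or inconsistent limit at the central laboratory, and not site-by-site choice of unit.

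Third, a reader might infer that the home-monitoring rule in 6.4.10.1 spreads the error to patient decisions. It does not. A high home reading leads to a same-day repeat and, if that is also high, to a central laboratory test; only the central value can end participation. A home reading inside the band can at most cause an extra test.

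Fourth, the four places agree with one another, so this is one repeated slip and not a contradiction between sections. That stands.

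Fifth, the upper count of 2.9 relies on an assumed mean of 180 and SD of 40, under which about 6.7% of patients (roughly 26 of 392) would exceed 240 mg/dL at one visit, and it uses the full unrounded band. That also stands: the count carries no weight beyond showing that the number is small.

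**Conclusion.** The point holds as a minor error. The printed 13.2 mmol/L is wrong for 240 mg/dL under every reasonable conversion factor, it occurs in four operative places, and it belongs to a withdrawal limit and not to background text. The two printed limits differ by about 2.2 mg/dL (237.8 against 240).

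The practical risk is confined to the central laboratory alert: set at >13.2 mmol/L, it would release the value and trigger withdrawal at about 238 to 240 mg/dL, where the mg/dL limit would not. Whether it was set that way cannot be seen from the protocol. Few or no patients are likely to be affected, a judgement that rests on the narrow band and on an assumed FPG distribution. Nothing here shows that any withdrawal decision would change, and sample size, alpha and the planned analysis are unaffected.

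**What to change.** Replace 13.2 with 13.3 mmol/L in all four places: the text of 3.1.1.4, Table 2, criterion 12 of 4.3.1, and 6.4.10.1. Confirm that the central laboratory alert is set to >240 mg/dL (>13.3 mmol/L). If the alert runs in mmol/L, compare at one decimal, because unrounded 13.3 mmol/L is 239.61 mg/dL and leaves a residual gap of 0.39 mg/dL.

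The cost is an administrative text correction in three sections and one check with the laboratory. Design, sample size and analysis do not change.
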